### **Data and Record Keeping:**

The hard copies of the Data Collection Form and questionnaires will be collected in the respective clinics of the three fellowship-trained orthopedic surgeons participating in the study. Data will be recorded on an SF-36 questionnaire form, an FAAM questionnaire form and a visual

analog scale. These questionnaires will be completed by the patient during their clinical visits. The questionnaire forms will be stored in their locked offices and collected by [name] every month. The data from the questionnaire will then be entered into a secure database. The questionnaire forms will be stored in the University of Wisconsin Department of Orthopedic Surgery research division offices. It will be held there for 7 years. The Data Collection Form attached to this document is an example of the form that the physician will complete at both the preoperative and postoperative patient visits.

Any future research wishing to utilize data from this study will need an IRB approved protocol, before they can access the data.

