#### **Specific Aims/Study Objectives:**

The major hypothesis of this study is that patient outcomes following Cartiva implantation will be non-inferior to those undergoing cheilectomy for patients with grade 2 hallux rigidus. Results will include the FAAM ADL and Sport Subscores, SF-36 scores, Visual analog pain scores and peak active dorsiflexion in the 2 patient populations. Additional results will include secondary

surgeries and adverse events. These will be evaluated pre-operatively and then post operatively at 2 weeks, 6 weeks, 3 months, 1 year and 2 year follow up. The 2 year follow up visit will be the primary end point of the study.

The primary objective of this study will be to evaluate the Cartiva procedure compared to the Cheilectomy with the above stated patient reported outcomes and physical exam measures. These two procedures are both indicated for the patient population selected in this study, however post-surgical results have never been compared to one another in current literature. The secondary objective will be to identify subsets of the study population which may be better suited for one of the two procedures. Through statistical analysis, we will attempt to identify patient variables that may impact the surgical response. This will allow surgeons to appropriately counsel their patients on which procedure they would benefit from.

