Following completion by the patient at each clinical visit, the Data Collection Form will be stored in the physician's secured office in a specified folder. [name] will collect the hard copy Data Collection Forms and questionnaires and enter them into the Department of Orthopedics and Rehabilitation's REDCap Database. After data entry, the Data Collection Forms will then be stored in a secure location through the Department of Orthopedic Surgery research division, where it will be held for 7 years.

When it comes to study timeline, a patient will be given the opportunity to enroll in the study at their initial consultation visit with one of the three board certified foot and ankle surgeons. If a patient has been diagnosed with Grade 2 hallux rigidus and is a surgical candidate, they will be given the opportunity to enroll in the study. If the patient desires to participate in the study, data will be collected from them at their initial consultation visit as described in the Data Collection Form. They will then undergo surgical intervention based on their randomization. Following surgery, they will follow up in clinic at 2 weeks, 6 weeks, 3 months and 1 year following surgery. These follow up visits are standard of care and would occur regardless of patient participation in

the study. At each visit, standard of care radiographs will be taken to evaluate the first MTP joint and the VAS, SF-36 and FAAM-ADL and Sports questionnaires will be completed specifically for research. The final study visit will be at 2 years post-surgery with final radiographs and questionnaires.

	Screening	Surgery	Week 2	Week 6	Month 3	Year 1	Year 2
Informed Consent	X						
Demographics and Medical/Surgical History	X						
Data Collection Form			X	X	X	X	X
Review of Imaging			X	X	X	X	X
Physical Exam			X	X	X	X	X

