### **Statistical Considerations:**

The primary hypothesis of the study is to show that long term (2 year) functional outcomes for those undergoing Cartiva are no worse than the long term functional outcomes for those undergoing Cheilectomy. The primary outcome is the FAAM – ADL subscore from baseline to 2 years post-surgery. The MCID of FAAM-ADL is 8 units and we assume the SD of the difference in FAAM – ADL from baseline to 2 years post-surgery is near 17 units. To have 80% power in a non-inferiority test under these assumptions, we would need to recruit 57 subjects per group. For those subjects that are lost-to-follow-up or have a subsequent surgery we will impute the missing 2 year follow-up value in two ways: 1) by LOCF (last observation carried forward) and 2) by mean 2 year follow-up value for those in the same surgical group. We will then examine results from both method as a sensitivity analysis of our imputation method. To further assist in ensuring enough patients in each group we will inflate our sample size to 60 per group for a total of 120 patients.

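### Cheap improvement: add a mail or electronic route for the self-completed FAAM-ADL when a patient misses the 2-year visit, which appears to fall outside standard of care

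*Combined protocol and SAP*

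**What the plan says.** Statistical Considerations defines the primary outcome as the FAAM-ADL "subscore from baseline to 2 years post-surgery". Specific Aims/Study Objectives fixes the time point: "The 2 year follow up visit will be the primary end point of the study".

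Collection is tied to attendance in two sections:

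- Data and Record Keeping: "These questionnaires will be completed by the patient during their clinical visits", and "The hard copies of the Data Collection Form and questionnaires will be collected in the respective clinics" of the three surgeons.
- Research Designs and Methods: the Data Collection Form is filed "Following completion by the patient at each clinical visit".

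No mail, telephone or electronic completion by patients is described, and neither is a procedure for a missed visit.

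On the status of the visits, Research Designs and Methods lists 2 weeks, 6 weeks, 3 months and 1 year and says "These follow up visits are standard of care and would occur regardless of patient participation in" the study. It then adds, separately: "The final study visit will be at 2 years post-surgery with final radiographs and questionnaires".

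Statistical Considerations imputes the 2-year value for patients lost to follow-up or with a subsequent surgery, once by LOCF and once by the 2-year mean of the same surgical group. On numbers, 57 per group are needed, and then: "To further assist in ensuring enough patients in each group we will inflate our sample size to 60 per group".

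**The concern.** The measurement that decides the trial is taken at what looks like the one follow-up visit without a routine clinical reason to attend, a year after the last routine one. FAAM-ADL, FAAM-Sports, SF-36 and VAS are all completed by the patient. Only dorsiflexion, the physical examination and radiographs need the patient in the clinic. Under the rule as written, a patient who would fill in a form at home but does not travel contributes no observed 2-year FAAM-ADL.

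That patient stays in the analysis, but with a substitute. LOCF supplies a score from 1 year or earlier for a 2-year endpoint. The group mean supplies no individual information and makes the standard error too small. In a non-inferiority test, a standard error that is too small makes it easier to declare non-inferiority wrongly. The sample size leaves little room for this.

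**Working it through.** **Inputs from the documents.** Margin 8 (the FAAM-ADL MCID), SD of change 17, power 80%, 57 per group raised to 60 (Statistical Considerations); 1:1 allocation (Research Designs and Methods).

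**Assumed.** True difference 0. Alpha and sidedness are not stated and are inferred in step 1. The proportion missing the 2-year visit is not given, so a range is shown.

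**1. Reproduce the plan's 57.** Normal approximation at one-sided 0.05:

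n = 2 × (1.645 + 0.842)² × 17² / 8² = 2 × 6.18 × 289 / 64 ≈ 55.8, so 56 per group.

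The exact noncentral t gives 57 (power 79.7% at 56, 80.3% at 57). At one-sided 0.025 the answers are 71 and 72. The plan's figure therefore implies one-sided 0.05.

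**2. Allowance.** 60 − 57 = 3 per arm, and 3/60 = 5%.

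**3. Power on observed scores.** With n observed per arm, SE = 17 × √(2/n), noncentrality = 8/SE, df = 2n − 2. For n = 60: SE = 3.104, noncentrality = 2.578, df = 118.

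| Missed at 2 years (assumed) | Observed per arm | Power, one-sided 0.05 |
|---|---|---|
| 0% | 60 | 82.1% |
| 5% | 57 | 80.3% |
| 10% | 54 | 78.4% |
| 15% | 51 | 76.3% |
| 20% | 48 | 74.0% |

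For example, if 20% missed the visit and remote forms recovered half of them, n would rise from 48 to 54 and power from 74.0% to 78.4%. The one-half is purely illustrative.

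**4. The allowance is shared.** Patients with a subsequent surgery are imputed too. The Data Safety and Monitoring Plan cites revision of 9% after Cartiva and 8–10% after cheilectomy; Background and Significance cites 5% at 5 years for Cartiva. If such rates applied by 2 years (an assumption), 5% to 10% of 60 is 3 to 6 patients per arm, which uses the 3 spare places with perfect attendance. Taking 5 per arm for revision, and assuming no overlap with missed visits, a further 10% missed (6) leaves 49 (74.8%) and 20% missed (12) leaves 43 (69.8%).

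**5. Imputation does not restore the information.** A simplified simulation replaced missing changes by the arm-mean change, with 60 per arm, values missing at random, the true difference at the margin and 40,000 runs. Type I error at nominal one-sided 0.05 was about 0.058 with 5% missing, 0.071 with 10% and 0.092 with 20%. The plan imputes the mean 2-year value, not the mean change, so these figures show the direction and rough size only.

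**The case against.** Several points on the other side stand.

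- **Status of the 2-year visit.** A reader might take it as stated that this visit is outside standard of care. The documents never say so, and the schedule table lists Year 2 like the other visits. It is the natural reading of where the standard-of-care list stops, but it is an inference.
- **The endpoint is not simply lost.** Data and Record Keeping does not say that the clinic is the only place where forms may be completed. Non-attenders remain in the analysis through two imputations, one of which is not a carried-forward score. What is lost is the observed 2-year value.
- **Entry criterion.** Patients unable to commit to follow-up appointments are excluded. This lowers the risk but gives no route when someone later fails to attend. Consent pages were not available, so any contact arrangements there cannot be judged.
- **Bias.** A reader might infer that missed visits bias the comparison, because attendance may depend on how the foot is doing. The documents offer no evidence of that. A biased between-group difference would generally need the dependence to differ by arm, and nothing gives a reason or direction.
- **Size.** The miss and recovery rates are assumed, and the power figures describe observed scores, not the planned imputed analysis. At 10% missed, power is under 2 points below the 80% target.
- **Subsequent surgery.** Remote forms cannot help patients imputed for that reason under the present rule. The thin allowance is therefore only partly an attendance problem.
- **VAS.** It is a mark on a 10 cm line measured in millimetres. A screen version would not be the same measurement, so REDCap cannot simply replace it. REDCap is described for entering paper forms, not for patient surveys.

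None of this argues for keeping attendance as the only described route to a form that the patient completes unaided.

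**Conclusion.** The point holds as a cheap improvement. In-clinic collection contradicts nothing in the plan and does not by itself invalidate the test. It does make the observed primary outcome depend on attending a visit that appears to be research-only, and it sends non-attenders to LOCF or group-mean values when a real score could often be obtained.

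The size cannot be fixed from the documents. For assumed miss rates of 10% to 20%, power on observed scores falls from 82% to between 78% and 74%, and lower if subsequent surgery also removes observed values. This rests on margin 8, SD 17, no true difference and the inferred one-sided 0.05. The documents support neither the claim that the endpoint is lost outright nor the claim that its comparison is shown to be biased.

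**What to change.** Amend the visit description in Research Designs and Methods and the collection rule in Data and Record Keeping as follows:

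- A patient who misses the 2-year visit (or the 1-year visit) completes FAAM-ADL, FAAM-Sports and SF-36 by mail or REDCap survey.
- The same patient completes the VAS on mailed paper printed so that the 10 cm line keeps its length.
- Scores obtained this way count as observed values, and the mode of completion is recorded.
- Only dorsiflexion, the physical examination and radiographs depend on attendance.

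The cost is a short IRB amendment, modest effort by existing staff to track and contact non-attenders, and setting up the mailing or survey. A small difference by mode is possible; because the mode is recorded, it can be checked. Treatment, endpoint and sample size are unchanged. The allowance for subsequent surgery and the choice of imputation method are separate matters that this change does not settle.

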## **Data Collection Form**

**Study ID:** \_\_\_\_\_

**Pre-operative Or Post-Operative Visit (How many weeks post op?):** \_\_\_\_\_

**Hallux Rigidus Grade:** \_\_\_\_\_

**FAAM-Sports Score:** \_\_\_\_\_

**FAAM-ADL Score:** \_\_\_\_\_

**VAS Score:** \_\_\_\_\_

**SF-36 Score:** \_\_\_\_\_

**1st MTP Peak Active Dorsiflexion:** \_\_\_\_\_

## **Pre-Operative Use Only**

**Gender:** \_\_\_\_\_

**BMI:** \_\_\_\_\_

# of Previous 1st MTP Procedures: \_\_\_\_\_

Current Smoker (Y/N): \_\_\_\_\_

**Post-Operative Use Only**

Evidence of Radiographic Implant Loosening (Y/N): \_\_\_\_\_

Evidence of Radiographic Osteolysis (Y/N): \_\_\_\_\_

Indication for Revision Procedure (Y/N): \_\_\_\_\_

*Visual Analog Scale (VAS)†*

## **Adverse Event Form:**

**Study ID:** \_\_\_\_\_

**Date of AE:** \_\_\_\_\_

**Title of AE:**

**Summary of AE:**

**Current Status of AE (Resolved, ongoing):****Action Taken Regarding AE:****FAAM Questionnaire**

Please Answer **every question** with **one response** that most closely describes your condition within the past week.

If the activity in question is limited by something other than your foot or ankle mark “Not Applicable” (N/A).

	No Difficulty	Slight Difficulty	Moderate Difficulty	Extreme Difficulty	Unable to do	N/A
Standing	Δ	Δ	Δ	Δ	Δ	Δ
Walking on even Ground	Δ	Δ	Δ	Δ	Δ	Δ
Walking on even ground without shoes	Δ	Δ	Δ	Δ	Δ	Δ
Walking up hills	Δ	Δ	Δ	Δ	Δ	Δ
Walking down hills	Δ	Δ	Δ	Δ	Δ	Δ
Going up stairs	Δ	Δ	Δ	Δ	Δ	Δ
Going down stairs	Δ	Δ	Δ	Δ	Δ	Δ
Walking on uneven ground	Δ	Δ	Δ	Δ	Δ	Δ
Stepping up and down curbs	Δ	Δ	Δ	Δ	Δ	Δ

Squatting	Δ	Δ	Δ	Δ	Δ	Δ
Coming up on your toes	Δ	Δ	Δ	Δ	Δ	Δ
Walking initially	Δ	Δ	Δ	Δ	Δ	Δ
Walking 5 minutes or less	Δ	Δ	Δ	Δ	Δ	Δ
Walking approximately 10 minutes	Δ	Δ	Δ	Δ	Δ	Δ
Walking 15 minutes or greater	Δ	Δ	Δ	Δ	Δ	Δ

Because of your foot and ankle how much difficulty do you have with:

	No Difficulty at all	Slight Difficulty	Moderate Difficulty	Extreme Difficulty	Unable to do	N/A
Home responsibilities	Δ	Δ	Δ	Δ	Δ	Δ
Activities of daily living	Δ	Δ	Δ	Δ	Δ	Δ
Personal care	Δ	Δ	Δ	Δ	Δ	Δ
Light to moderate work (standing, walking)	Δ	Δ	Δ	Δ	Δ	Δ
Heavy work (push/pulling, climbing, carrying)	Δ	Δ	Δ	Δ	Δ	Δ
Recreational activities	Δ	Δ	Δ	Δ	Δ	Δ

How would you rate your current level of function during you usual activities of daily living from 0 to 100 with 100 being your level of function prior to your foot or ankle problem and 0 being the inability to perform any of your usual daily activities.

— . 0 %

Because of your foot and ankle how much difficulty do you have with:

	No Difficulty at all	Slight Difficulty	Moderate Difficulty	Extreme Difficulty	Unable to do	N/A
Running	Δ	Δ	Δ	Δ	Δ	Δ
Jumping	Δ	Δ	Δ	Δ	Δ	Δ
Landing	Δ	Δ	Δ	Δ	Δ	Δ
Starting and stopping quickly	Δ	Δ	Δ	Δ	Δ	Δ
Cutting/lateral Movements	Δ	Δ	Δ	Δ	Δ	Δ
Ability to perform Activity with your Normal technique	Δ	Δ	Δ	Δ	Δ	Δ
Ability to participate In your desired sport As long as you like	Δ	Δ	Δ	Δ	Δ	Δ

How would you rate your current level of function during your sports related activities from 0 to 100 with 100 being your level of function prior to your foot or ankle problem and 0 being the inability to perform any of your usual daily activities?

— — — . 0%

Overall, how would you rate your current level of function?

█ Normal    Δ Nearly Normal    Δ Abnormal    Δ Severely Abnormal

# 36-Item Short Form Survey Instrument (SF-36)

## RAND 36-Item Health Survey 1.0 Questionnaire Items

**Choose one option for each questionnaire item.**

1. In general, would you say your health is:

- 1 - Excellent
- 2 - Very good
- 3 - Good
- 4 - Fair
- 5 - Poor

---

2. **Compared to one year ago**, how would you rate your health in general **now**?

- 1 - Much better now than one year ago
- 2 - Somewhat better now than one year ago
- 3 - About the same
- 4 - Somewhat worse now than one year ago
- 5 - Much worse now than one year ago

---

The following items are about activities you might do during a typical day. Does **your health now limit you** in these activities? If so, how much?

	Yes, limited a lot	Yes, limited a little	No, not limited at all
3. Vigorous activities , such as running, lifting heavy objects, participating in strenuous sports	 1	 2	 3
4. Moderate activities , such as moving a table, pushing a vacuum cleaner, bowling, or playing golf	 1	 2	 3
5. Lifting or carrying groceries	 1	 2	 3
6. Climbing several flights of stairs	 1	 2	 3
7. Climbing one flight of stairs	 1	 2	 3
8. Bending, kneeling, or stooping	 1	 2	 3
9. Walking more than a mile	 1	 2	 3
10. Walking several blocks	 1	 2	 3
11. Walking one block	 1	 2	 3
12. Bathing or dressing yourself	 1	 2	 3

During the **past 4 weeks**, have you had any of the following problems with your work or other regular daily activities **as a result of your physical health?**

	Yes	No
13. Cut down the amount of time you spent on work or other activities		
	1	2
14. Accomplished less than you would like		
	1	2
15. Were limited in the kind of work or other activities		
	1	2
16. Had difficulty performing the work or other activities (for example, it took extra effort)		
	1	2

---

During the **past 4 weeks**, have you had any of the following problems with your work or other regular daily activities **as a result of any emotional problems** (such as feeling depressed or anxious)?

Yes      No

17. Cut down the **amount of time** you spent on work or other activities       1       2

18. **Accomplished less** than you would like       1       2

19. Didn't do work or other activities as **carefully** as usual       1       2

---

20. During the **past 4 weeks**, to what extent has your physical health or emotional problems interfered with your normal social activities with family, friends, neighbors, or groups?

- 1 - Not at all
- 2 - Slightly
- 3 - Moderately
- 4 - Quite a bit
- 5 - Extremely

---

21. How much **bodily** pain have you had during the **past 4 weeks**?

- 1 - None
- 2 - Very mild
- 3 - Mild
- 4 - Moderate
- 5 - Severe
- 6 - Very severe

---

22. During the **past 4 weeks**, how much did **pain** interfere with your normal work (including both work outside the home and housework)?

- 1 - Not at all
- 2 - A little bit
- 3 - Moderately
- 4 - Quite a bit
- 5 - Extremely

---

These questions are about how you feel and how things have been with you **during the past 4 weeks**. For each question, please give the one answer that comes closest to the way you have been feeling.

How much of the time during the **past 4 weeks**...

	All of the time	Most of the time	A good bit of the time	Some of the time	A little of the time	None of the time
23. Did you feel full of pep?	 1	 2	 3	 4	 5	 6
24. Have you been a very nervous person?	 1	 2	 3	 4	 5	 6
25. Have you felt so down in the dumps that nothing could cheer you up?	 1	 2	 3	 4	 5	 6
26. Have you felt calm and peaceful?	 1	 2	 3	 4	 5	 6
27. Did you have a lot of energy?	 1	 2	 3	 4	 5	 6
28. Have you felt downhearted and blue?	 1	 2	 3	 4	 5	 6
29. Did you feel worn out?	 1	 2	 3	 4	 5	 6
30. Have you been a happy person?	 1	 2	 3	 4	 5	 6
31. Did you feel tired?	 1	 2	 3	 4	 5	 6

---

32. During the **past 4 weeks**, how much of the time has **your physical health or emotional problems** interfered with your social activities (like visiting with friends, relatives, etc.)?

---

- 1 - All of the time
- 2 - Most of the time
- 3 - Some of the time
- 4 - A little of the time
- 5 - None of the time

How TRUE or FALSE is **each** of the following statements for you.

	Definitely true	Mostly true	Don't know	Mostly false	Definitely false
33. I seem to get sick a little easier than other people	 1	 2	 3	 4	 5
34. I am as healthy as anybody I know	 1	 2	 3	 4	 5
35. I expect my health to get worse	 1	 2	 3	 4	 5
36. My health is excellent	 1	 2	 3	 4	 5

---

## ABOUT

The RAND Corporation is a research organization that develops solutions to public policy challenges to help make communities throughout the world safer and more secure, healthier and more prosperous. RAND is nonprofit, nonpartisan, and committed to the public interest.

[name]

[name]

---

RAND® is a registered trademark. Copyright © 1994-2016 RAND Corporation
